# 4.3 Study Endpoints

### 4.3.1 Primary Endpoint

Comparison between ASTX727 and IV decitabine:

• Total 5-day AUC exposures of decitabine after treatment with ASTX727 versus IV decitabine.

# 4.3.2 Secondary Endpoints

- Safety as assessed by AEs, concomitant medications, physical examination, clinical laboratory tests (hematology, serum chemistry, and urinalysis), vital signs, Eastern Cooperative Oncology Group (ECOG) performance status, and electrocardiogram (ECG).
- Maximum %LINE-1 demethylation.
- Additional secondary PK parameters.
- Clinical response (complete response [CR], marrow complete response [mCR], partial response (PR), and hematologic improvement [HI]) based on International Working Group (IWG) 2006 MDS response criteria.
- Red blood cell (RBC) or platelet transfusion independence (TI).

- Leukemia-free survival, defined as the number of days from the date of randomization to the date when bone marrow or peripheral blood blasts reach ≥20%, or death from any cause.
- Overall survival (OS), defined as the number of days from the date of randomization to the date of death from any cause.

# 4.4 Study Steering Committee

The Study Steering Committee (SSC) will comprise the principal investigators (or designees), medical monitor, study director, PK director, and other study team members as appropriate and will review available clinical data on a predetermined schedule. The SSC may recommend changes to the study based on emerging data.

### 5.0 SELECTION AND WITHDRAWAL OF SUBJECTS

# 5.1 Number of Subjects and Centers

Approximately 132 (at least 118 evaluable) subjects will be enrolled in this study at approximately 60 study centers in North America.

### 5.2 Inclusion Criteria

To be eligible for the study, subjects must fulfill all of the following inclusion criteria:

- 1) Able to understand and comply with the study procedures, understand the risks involved in the study, and provide legally effective informed consent before the first study-specific procedure; specifically able to comply with the PK assessment schedule during the first 2 treatment cycles.
- 2) Men or women ≥18 years who are candidates to receive IV decitabine, ie, subjects with MDS previously treated or untreated, with de novo or secondary MDS, including all French-American-British subtypes (refractory anemia, refractory anemia with ringed sideroblasts, refractory anemia with excess blasts, refractory anemia with excess blasts in transformation, and CMML), and subjects with MDS IPSS int-1, -2, or high-risk MDS.
- 3) ECOG performance status of 0 to 1.
- 4) Adequate organ function defined as follows:
  - a) Hepatic: Total or direct bilirubin  $\leq$ 2 × upper limit of normal (ULN); AST/SGOT and ALT/SGPT  $\leq$ 2.5 × ULN.
  - b) Renal: serum creatinine ≤1.5 × ULN or calculated creatinine clearance or glomerular filtration rate >50 mL/min/1.73 m² for subjects with creatinine levels above institutional normal.
- 5) No major surgery within 30 days of first study treatment.
- 6) Life expectancy of at least 3 months.

- 7) Women of child-bearing potential must not be pregnant or breastfeeding and must have a negative pregnancy test at screening. Women of non-childbearing potential are those who have had a hysterectomy or bilateral oophorectomy, or who have completed menopause, defined as no menses for at least 1 year AND either age ≥65 years or follicle-stimulating hormone levels in the menopausal range.
- 8) Subjects and their partners with reproductive potential must agree to use effective contraceptive measures during the study and for 3 months after the last dose of study treatment. Effective contraception includes methods such as oral contraceptives or double-barrier method (eg, use of a condom AND diaphragm, with spermicide).

### 5.3 Exclusion Criteria

Subjects meeting any of the following criteria will be excluded from the study:

- 1) Prior treatment with more than 1 cycle of azacitidine or decitabine.
- 2) Hospitalization for more than 2 days for documented febrile neutropenia, pneumonia, sepsis, or systemic infection in the 30 days before screening.
- 3) Treatment with any investigational drug or therapy within 2 weeks of study treatment, or 5 half-lives, whichever is longer, before the first dose of study treatment, or ongoing clinically significant adverse events (AEs) from previous treatment.
- 4) Cytotoxic chemotherapy or prior azacitidine or decitabine within 4 weeks of first dose of study treatment.
- 5) Concurrent MDS therapies, including lenalidomide, erythropoietin, cyclosporine/tacrolimus, granulocyte-colony stimulating factor (G-CSF), granulocyte-macrophage colony-stimulating factor, etc. (Prior treatment with these agents is permitted, provided that completion is at least 1 week before the first dose of study treatment.)
- 6) Poor medical risk because of other conditions such as uncontrolled systemic diseases, active uncontrolled infections, or comorbidities that may put the patient at risk of not being able to complete at least 2 cycles of treatment.
- 7) Known significant mental illness or other condition, such as active alcohol or other substance abuse or addiction, that in the opinion of the investigator predisposes the subject to high risk of noncompliance with the protocol.
- 8) Rapidly progressive or highly proliferative disease (total white blood cell count of  $>15 \times 10^9/L$ ) or other criteria that render the subject at high risk of requiring intensive cytotoxic chemotherapy within the next 3 months.
- 9) Life-threatening illness or severe organ system dysfunction, such as uncontrolled congestive heart failure or chronic obstructive pulmonary disease, or other reasons including laboratory abnormalities, which, in the investigator's opinion, could compromise the subject's safety, interfere with the absorption or metabolism of ASTX727, or compromise completion of the study or integrity of the study outcomes.

- 10) Prior malignancy, except for adequately treated basal cell or squamous cell skin cancer, in situ cervical cancer, prostate cancer or breast cancer under control with hormone therapy, or other cancer from which the subject has been disease free for at least 2 years.
- 11) Hypersensitivity to decitabine, cedazuridine, or any of the excipients in ASTX727 tablets or IV decitabine.

# 5.4 Treatment Discontinuation and Withdrawal of Subjects

Subjects who discontinue study treatment will be followed up for important study data, as described below, unless they withdraw consent from further follow up.

Astex Pharmaceuticals may stop the study at any time. In this event, Astex will make reasonable efforts to ensure subjects are appropriately transitioned off study.

# 5.4.1 Discontinuation from Study Treatment

Contact the Astex medical monitor before discontinuing treatment for a given subject.

Subjects who discontinue study treatment at any time will be followed for safety (Section 10.2).

Subjects will be followed for survival/conversion to AML according to Section 9.5.6.

- Investigators can discontinue subjects from study treatment in case of unacceptable toxicity, non-compliance, disease progression requiring alternative therapy, or if the investigator determines it is in the subject's best interest.
- Astex Pharmaceuticals may require that a subject is discontinued from treatment for safety reasons or for noncompliance.

Notwithstanding the above, every attempt should be made for subjects to complete at least the first 2 cycles of treatment and the corresponding PK assessments to minimize the number of non-evaluable subjects and safeguard the integrity of the study primary endpoint.

In all cases, the reason(s) for discontinuation from study treatment must be recorded in the source document and on the relevant page of the subject's electronic case report form (eCRF).

# 5.4.2 Withdrawal from the Study

Subjects may withdraw consent for the study at any time; the specific reason for withdrawal must be obtained. It is important to obtain follow-up information, according to standard medical practice, on any subject who prematurely withdraws from the study. Every effort must be made to obtain at least the assessments that are critical for efficacy or safety evaluation (eg, disease response, survival, safety assessments), unless the subject withdraws consent from further follow up.

# 5.4.3 Replacement of Subjects

Enrollment of subjects will continue until the required number of 118 evaluable subjects is reached.

# 6.0 ENROLLMENT, RANDOMIZATION, AND BLINDING PROCEDURES

After providing legally effective informed consent, subjects will be screened at each study center for assessment of study eligibility. Eligibility will be further confirmed by the medical monitor prior to randomization of the subject. At screening, each subject will be assigned a unique number (subject identification [ID] number) consisting of 6 digits; the first 3 digits will reflect the study center number, followed by a 3-digit number corresponding to the individual subject. The ID will be used to identify the subject throughout the study and will be entered on all study documents.

## 6.1 Randomization

Eligible subjects will be randomly assigned to Cycle 1 study treatment in a ratio of 1:1 to receive ASTX727 or IV decitabine. Subjects will cross over to the other therapy in Cycle 2. Treatment assignment will be determined through a computer-generated randomization schedule and accessed through an interactive voice response system. Subjects should receive study treatment as soon as possible after randomization.

# 6.2 Blinding

This is an open-label study. Treatment assignment will be unblinded.

# 7.0 STUDY TREATMENTS

# 7.1 Investigational Medicinal Product (IMP) – ASTX727

ASTX727 (recently approved as INQOVI®) is a film-coated, oval, immediate-release FDC tablet containing the combination of cedazuridine (100 mg) and decitabine (35 mg) for oral administration. The tablets are packed as a 5-count in an opaque high-density polyethylene (HDPE) bottle with a child resistant closure. Please see the ASTX727 IB and Pharmacy Manual (provided by Astex) for more information.

### 7.2 IV Decitabine

Decitabine, 20 mg/m^2 IV will be used as the reference product. Decitabine is approved for IV infusion in the US and will be sourced locally at the US study centers. Decitabine for IV infusion will be provided by the sponsor as an IMP in territories where it is not currently approved for use.

# 7.3 Study Treatment Storage

ASTX727 tablets should be stored on site as indicated in the study-specific Pharmacy Manual according to institutional policy and the Sponsor's requirements. ASTX727 tablets for outpatient administration should be dispensed by the study pharmacist according to institutional policy and

in accordance with the Sponsor's requirements. Instructions regarding transport from pharmacy to home and at-home storage instructions should be given to the study subject, as applicable.

Decitabine should be stored according to institutional policy and storage instructions provided in the US product package insert (current Dacogen Prescribing Information).

Records of the receipt and dispensing of study drug supplies will be kept at the study centers and reconciled at the end of the study to provide a complete accounting of all used and unused drug supplies.

# 7.4 Study Treatment Administration

The dosing regimen for this study is shown in Table 5. Subjects will receive the ASTX727 FDC tablet Daily×5 in Cycle 1, followed by a 1-hour infusion of IV decitabine 20 mg/m² Daily×5 in Cycle 2, or the converse order. In Cycles ≥3, subjects will receive the ASTX727 tablet Daily×5 in 28-day cycles.

Reconstitution of decitabine for IV administration will be performed by the institutional pharmacists according to the US package insert.

Subjects will be required to fast from food for 4 hours on days in all cycles when receiving ASTX727. Fasting begins at least 2 hours prior to and ends 2 hours after dosing. Subjects will take ASTX727 with ~240 mL (8 fluid oz) of water. Clear liquids such as water, black coffee, or tea may be allowed as desired together with any concomitant medication that is needed to be given to the subject. ASTX727 should be taken at the same time of day (8 AM  $\pm 1$  hour) on each dosing day during the first 2 cycles. In subsequent cycles, ASTX727 should be taken at the same time of day ( $\pm 1$  hour) on dosing days. For late or missed (or vomited) doses, see Section 7.5.

Table 5: Dosing Schedule by Day and Cycle

| Cycle (28 Days)                                  |   | 1 |   |   |   |      |   |   | 2 |   |   |      |   | 2 | ≥3 |   |   |      |  |
|--|---|---|---|---|---|------|---|---|---|---|---|------|---|---|----|---|---|------|--|
| Cycle Day  | 1 | 2 | 3 | 4 | 5 | 6-28 | 1 | 2 | 3 | 4 | 5 | 6-28 | 1 | 2 | 3  | 4 | 5 | 6-28 |  |
| If randomized to ASTX727 in Cycle 1, then:       |   |   |   |   |   |      |   |   |   |   |   |      |   |   |    |   |   |      |  |
| ASTX727 tablet                                   | × | × | × | × | × |      |   |   |   |   |   |      | × | × | ×  | × | × |      |  |
| IV decitabine (20 mg/m  )            |   |   |   |   |   |      | × | × | × | × | × |      |   |   |    |   |   |      |  |
| If randomized to IV decitabine in Cycle 1, then: |   |   |   |   |   |      |   |   |   |   |   |      |   |   |    |   |   |      |  |
| ASTX727 tablet                                   |   |   |   |   |   |      | × | × | × | × | × |      | × | × | ×  | × | × |      |  |
| IV decitabine (20 mg/m  )            | × | × | × | × | × |      |   |   |   |   |   |      |   |   |    |   |   |      |  |

NOTE: On days of ASTX727 administration, subjects should take the FDC tablet at the same time each day  $\pm 1$  hour (8 AM during the first 2 cycles).

### 7.5 Late or Missed ASTX727 Doses

# 7.5.1 Cycle 1 or 2

In the ASTX727 cycle (1 or 2), subjects should take the FDC tablet at the same time of day (8 AM  $\pm$  1 hour) on each day of ASTX727 administration. If the tablet is taken within 3 hours after 8 AM, proceed with dosing and PK sample collection (if applicable) according to Table 6. (A dose administered within 3 hours after 8 AM will not be considered a protocol deviation.) If the tablet is taken more than 3 hours after 8 AM, the PK for that day may not be evaluable. Contact the medical monitor for instructions regarding whether the PK sampling schedule may be adjusted on the following days (if applicable).

If the subject vomits within 6 hours after dosing on a dosing day, the PK for that day and the following day (if applicable) may not be evaluable. Contact the medical monitor for instructions regarding whether the PK sampling schedule may be adjusted in remaining days of dosing (if applicable).

# 7.5.2 Cycles ≥3

If an ASTX727 dose is not taken at the intended time on a dosing day, the dose should be taken immediately if the subject remembers by 6:00 PM that day. After 6:00 PM, the dose should be skipped, and dosing should resume the following day at the intended time. Subjects should complete all 5 daily doses; if a dose is missed, the dosing period will extend by one day for every missed dose to complete the 5 daily doses. A vomited dose should not be retaken. Dosing should resume on the next dosing day and continue for the remaining dosing days in the cycle. If the subject experienced repeated vomiting after dosing in Cycles 1 or 2, a prophylactic antiemetic should be considered for the subsequent cycles.

# 7.6 Guidelines for Adjusting or Withholding Study Treatment

It is important that Cycles 1 and 2 are given at full dose (safely) to allow for proper assessment of exposure after ASTX727 and IV decitabine administration. Contact the Astex medical monitor if considering reducing the dose in the first 2 cycles.

Dose delays up to 2 weeks for recovery of blood counts from drug-related myelosuppression are acceptable. Delays beyond 2 weeks in the first 2 cycles must be approved by the medical monitor. Subjects whose therapy is interrupted during dosing days of ASTX727 in the first 2 cycles may not be evaluable for assessment of the primary endpoint unless treatment can be restarted on a later date (after agreement by the medical monitor) in a manner that will allow AUC assessment (see Section 11.2.2 and Section 11.6). Dosing should be delayed in the presence of non-hematologic toxicities (serum creatinine equal or greater than 2 mg/dL; SGPT or bilirubin equal or greater than 2 times the ULN), or active or uncontrolled infection until these toxicities are resolved.

Beginning with Cycle 3, dose delays to allow recovery of blood counts from drug-related myelosuppression are allowed at the discretion of the investigator. If there is a need for dose

reduction starting from Cycle 3, ASTX727 treatment may be reduced to 4 days. Additional dose reductions may be applied by further reducing treatment to 3 days. Dose reductions should be considered if myelosuppression is suspected to be drug-related rather than disease-related. Transient reductions in blood counts on Day 15 (expected maximal drug effect) followed by a recovery trend by Day 28 may be indicative of a drug-related effect, whereas stable counts or improvements in counts by Day 15 followed by reduction by Day 28 is indicative of a disease effect that is being improved by the drug on Day 15. In the event of drug-related count suppression, a dose reduction in consultation with the medical monitor may be considered to allow the patient to achieve a complete or partial response.

### 7.7 Concomitant Treatment

Record on the concomitant medication eCRF all treatments a subject receives, including supportive or palliative treatment whether prescription or over the counter, vitamin and mineral supplements, herbs, and medications taken for procedures (eg, biopsy). Also record antacids, proton pump inhibitors, and H2 antagonists. Specifically record start/stop dates, name of treatment, and indication for use.

# 7.7.1 Supportive, Prophylactic, or Other Treatments

The investigator is permitted to perform diagnostic testing and to prescribe supportive treatment(s) at his or her discretion. Appropriate hydration and supportive care (eg, antiemetics and blood and platelet transfusions) may be administered according to study center standards. Ensure the subject is adequately hydrated.

All supportive treatment including units of blood and platelet transfusions must be recorded on the eCRF. Aggressive surveillance, prophylaxis, and the treatment of bacterial, fungal, viral, and opportunistic infections are essential to prevent morbidity and mortality.

Antibiotics may be used to prevent or manage febrile neutropenia according to institutional standard practice. Febrile neutropenia is defined as temperature at least 38.5°C when the absolute neutrophil count (ANC) is <1000 cells/μL. Febrile subjects are to be evaluated by physical examination, complete blood count (CBC) with differential, chest x-ray, urine culture, and blood culture. Subjects with febrile neutropenia or frank infection are to be hospitalized for temporizing antibiotic coverage, consistent with local pathogen sensitivities until an infectious agent is identified. Antibiotic prophylaxis (at least a quinolone unless either medically contraindicated or contrary to institutional standard practice) is strongly recommended for subjects with documented ANC <0.5×10^9/L or expected to experience ANC <0.5×10^9/L for any duration during the first 2 cycles. In subsequent cycles, antibiotic prophylaxis is strongly recommended for subjects expecting to experience ANC <0.5×10^9/L for more than 7 days or per local institutional guidelines. The medical monitor should be consulted in cases where specific antibiotics are contraindicated. Fungal prophylaxis is strongly recommended for subjects expected to experience ANC <0.5×10^9/L for more than 7 days during any cycle or per local institutional guidelines.

Hematopoietic growth factors will not be routinely used. However, short-term use of G-CSF for febrile neutropenia is permitted at the discretion of the treating physician and should be guided by accepted practice or institutional guidelines.

### 7.7.2 Prohibited Medications

Prohibited concomitant therapies while on study are as follows: chemotherapy, immunotherapy, or any experimental therapy.

Also prohibited are other nucleosides or drugs that are metabolized by CDA (including cytarabine, gemcitabine, azacitidine, vidarabine, zalcitabine, zidovudine, telbivudine, didanosine, zalcitabine, stavudine, lamivudine, abacavir, emtricitabine, entecavir, apricitabine, idoxuridine, trifluridine, tenofovir and adefovir).

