### Hematological Improvement (HI): lasts at least 8 weeks

Erythroid Response (HI-E): Major Response: Hemoglobin increase ≥1.5 g/dL in the absence of RBC

transfusions.

Platelet Response (HI-P): Major Response: Absolute increase of platelet count from <20 to >20 X 10^9/L and

by at least 100%, or if more than  $20 \times 10^9$ /L, by an absolute increase of at least  $30 \times 10^9$ /L in the absence of platelet

transfusions.

Neutrophil Response (HI-N): Major Response: granulocyte increase ≥100%, and by an absolute increase ≥0.5 x

 $10^{9}/L$ .

a Abnormal baseline counts should be assessed within one week prior to therapy, not influenced by transfusions (no transfusion for at least 1 week).

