# 11.7.2 Transfusion Independence

Transfusion independence (TI) will be analyzed separately for platelet and RBC TI, the latter defined as no RBC transfusion for 56 consecutive days while maintaining hemoglobin  $\geq 8$  g/dL. Platelet TI is defined as no platelet transfusion for 8 consecutive weeks, while maintaining platelets  $\geq 20 \times 10^9$ /L. Transfusion independence rates will be calculated based on subjects who are in the Efficacy Analysis Set and who were transfusion dependent at baseline. The 95% Wald CIs will be provided separately for the RBC and platelet TI rates.

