### **7.6.3 Concomitant Medications**

Concomitant medications are medications taken with a start date on or after the date of the first dose of study treatment, or those with a start date before the start of the administration of study treatment and a stop date on or after the start of the administration of study treatment. Medications taken beyond 30 days from the last dose of study treatment or after the start of a post-treatment alternative anti-leukemia treatment are not considered concomitant medications, unless they are used for treating a related SAE. For the purpose of inclusion in the concomitant medication tables, incomplete medication start and stop dates will be imputed conservatively following the data programming conventions as detailed in the Astex Data Programming Standards.

Concomitant medication will be coded by the latest version of WHO Drug Dictionary before the data download and summarized by Anatomical Therapeutic Chemical (ATC level 2) and drug name, sorted alphabetically, using counts and percentages.

Special interest concomitant medications include anti-emetic drugs, growth factors (including G-CSF, GM-CSF and ESAs), anti-infective medications (including but not limited to anti-bacterials, anti-mycotics, anti-mycobacterials, anti-virals and immunoglobulins) and hydroxyurea given to reduce high counts during study treatment and not as part of a subsequent anti-leukemia treatment. These concomitant medications will be tabulated separately.

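### Erythroid improvement and RBC transfusion independence are counted without regard to other MDS therapies, which are excluded at entry but not clearly excluded on study

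*Protocol*

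**What the plan says.** **Entry.** Criterion 5 in protocol Section 5.3 excludes "Concurrent MDS therapies, including lenalidomide, erythropoietin, cyclosporine/tacrolimus, granulocyte-colony stimulating factor (G-CSF), granulocyte-macrophage colony-stimulating factor, etc". Earlier use is acceptable if it ended at least 1 week before the first dose.

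**On study.** Section 7.7.2 reads "Prohibited concomitant therapies while on study are as follows: chemotherapy, immunotherapy, or any experimental therapy", and adds nucleosides and other drugs metabolized by CDA. It names none of the criterion 5 agents and has no class for other MDS therapy. Section 7.7.1 says "Hematopoietic growth factors will not be routinely used", with one stated exception: "short-term use of G-CSF for febrile neutropenia is permitted at the discretion of the treating physician".

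**Endpoints.** In Table 8, HI-E is "Hemoglobin increase ≥1.5 g/dL in the absence of RBC" transfusions, lasting at least 8 weeks. HI-P carries the matching condition on platelet transfusions. HI-N carries no condition on growth factors. Protocol Section 11.7.2 defines RBC TI as "no RBC transfusion for 56 consecutive days while maintaining hemoglobin" at 8 g/dL or above. SAP Section 7.5.4 uses the same rule and extends it to 84 and 112 days.

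**Analysis.** The Efficacy Analysis Set (protocol 11.2.3) keeps all data whatever the protocol violations. Section 11.7 analyzes efficacy as a single group. SAP Section 7.6.3 tabulates separately, as medications of special interest, "growth factors (including G-CSF, GM-CSF and ESAs" among other classes.

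**Scope of the SAP.** SAP Section 1.0 states that it covers AML subjects only and that a separate, earlier-approved SAP covers MDS/CMML.

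**The concern.** By listing these drugs in criterion 5, the protocol itself treats them as MDS therapies that compete with the study drug. An exclusion criterion acts at entry. After that, a hemoglobin response needs protection either from a clear on-study restriction or from a counting rule in the endpoint. The restriction is soft for ESAs and unclear for the other agents. The counting rule addresses transfusion only.

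HI and TI are secondary efficacy endpoints with no control. From Cycle 3 every subject receives ASTX727, so an effect of an added drug cannot cancel between groups. To the extent that such a drug raises hemoglobin, the reported rate is too high as a measure of ASTX727 activity. Protocol Sections 4.1 and 4.2 describe the clinical endpoints as essential and link the efficacy data to the marketing application, so the rates will be used.

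**Working it through.** The plan gives no figure for HI or TI, so there is nothing to reproduce on this point. The protocol's calculated sample size (118 evaluable, 90% power) concerns the AUC test and is not touched.

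**Step 1. Entry rule against on-study rule, by agent.**

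| Agent | Criterion 5 | 7.7.2 | 7.7.1 |
|---|---|---|---|
| Erythropoietin | Named | Not named | Discouraged as a growth factor; no ban, no stated exception |
| Lenalidomide, cyclosporine/tacrolimus | Named | Covered only if chemotherapy or immunotherapy includes them; neither term is defined | Not mentioned |
| G-CSF | Named | Not named | Discouraged; short-term use for febrile neutropenia permitted |
| GM-CSF | Named | Not named | Discouraged; no stated exception |

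**Step 2. One case through the rules.** Take a subject who is RBC-transfusion dependent at baseline and starts an ESA in Cycle 3. Hemoglobin rises by 1.5 g/dL, to above 8 g/dL, and stays there for 8 weeks without RBC transfusion.

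- HI-E (Table 8): met.
- RBC TI (11.7.2): met at 56 days.
- Analysis set (11.2.3): the data stay in even if the ESA use was logged as a violation.
- Reporting (11.7): the subject is one responder in a pooled rate.

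**Step 3. Rules elsewhere for the same event.** SAP 7.5.3 ends response duration at alternative therapy, and SAP 7.5.7 counts alternative anti-leukemia therapy as an EFS event; both except transplantation. Protocol 10.2 and 11.8 end AE recording and the TEAE window when new MDS/CMML treatment starts. Neither protocol 11.7.1 and 11.7.2 nor SAP 7.5.4 has a parallel rule for HI or TI.

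**Step 4. Possible size.** The documents give no rate of use and no response rate, so every input here is an assumption.

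- Inflation = u × g, where u is the share of the denominator that starts an agent and g is the share of users who gain the response because of it. With u = 0.10 to 0.20 and g = 0.20 to 0.40: 0.10 × 0.20 = 0.02, and 0.20 × 0.40 = 0.08. That is 2 to 8 points.
- Allowing for users who would have responded anyway: inflation = (1 − p) × u × r, where p is the true rate and r is the share of would-be non-responders converted. With p = 0.20 to 0.40, u = 0.05 to 0.20 and r = 0.20 to 0.40: lowest (1 − 0.40) × 0.05 × 0.20 = 0.006; highest (1 − 0.20) × 0.20 × 0.40 = 0.064. That is 0.6 to 6.4 points.

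Together this is about 1 to 8 points. For scale, the 95% Wald half-width is 1.96 × √(p(1 − p)/n). At n = 132 it is 6.8 points for p = 0.20 and 8.4 points for p = 0.40. The TI denominator is only the subjects dependent at baseline. The documents do not give that number; at an assumed n = 60 and p = 0.40 the half-width is 12.4 points. The bias is thus within sampling error in most of these scenarios, but the confidence interval does not allow for it.

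**The case against.** **The governing SAP for HI is not to hand.** HI is an MDS/CMML endpoint, and protocol Section 11.0 defers analysis detail to the SAP. A rule may sit in the MDS/CMML SAP. This stands: the absence is shown only for the protocol and the AML SAP.

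**A reader might infer that erythropoietin and lenalidomide are simply allowed on study.** The documents do not support that. Section 7.7.1 discourages growth factors and gives no exception for erythropoietin, and the prohibited classes in 7.7.2 may cover the other agents. The defect is ambiguity, not permission. Nor does the ESA table in the SAP show that use is expected. It is a planned summary for AML subjects under European and Canadian amendments whose concomitant-treatment sections were not available.

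**Follow-up may stop first.** Progression requiring alternative therapy is a ground for stopping study treatment (5.4.1). The 30-day visit moves to within 3 days before new anti-cancer treatment if that comes sooner (9.5.5), and it holds the final transfusion assessment (Table 9). If lenalidomide counts as new anti-cancer treatment, a further 56-day window on it would seldom be captured. This weakens the lenalidomide case. It does not reach an ESA given as support while ASTX727 continues.

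**HI-N is weakly exposed.** The only stated allowance is short-term G-CSF, and HI must last 8 weeks. Voiding any HI-N window that contains a few days of G-CSF would erase genuine responses. This stands and shapes the fix.

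**Counting all observed data is a legitimate choice.** It is, if stated as such. The resulting rate then describes ASTX727 plus whatever else was given, and the plan does not say so.

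**Conclusion.** The concern holds in limited form. Followed as written, the HI-E and RBC TI rules in the protocol, and the RBC TI rule in the AML SAP, credit ASTX727 with a response obtained on an ESA or another MDS therapy. No comparator or confidence interval corrects for this. The on-study restriction is too loose or unclear to close the gap.

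The size is unknown. About 1 to 8 percentage points follows from assumed uptake of 5 to 20% and assumed attributable response of 20 to 40%, not from any figure in the documents. A reader might infer that the reported rates are in fact inflated. The documents do not show that, because they contain no data on use of these drugs. The endpoints affected are secondary and descriptive; the AUC equivalence analysis does not depend on them. The conclusion would change if the MDS/CMML SAP already contains a handling rule.

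**What to change.** First check the MDS/CMML SAP for an existing rule. If there is none:

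- In protocol 11.7.1 and 11.7.2, and for RBC TI in SAP 7.5.4, count an 8-week HI-E window or a 56-, 84- or 112-day RBC TI window as a response only if the concomitant-medication eCRF shows no ESA or other non-study MDS or anti-leukemia therapy during that window. Windows completed before such an agent starts still count. List the agents, and report the all-data rate alongside.
- For HI-N, do not void a window for brief permitted G-CSF. Require that the qualifying neutrophil counts were not obtained during G-CSF use, or report HI-N with and without G-CSF-exposed subjects.
- Separately, the sponsor must reconcile criterion 5 with Sections 7.7.1 and 7.7.2. Which agents may be used on study is for its clinical team.

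The cost is a few sentences and a programming join to drug names, start and stop dates and indications already collected under protocol Section 7.7. The HI-E and RBC TI rates may come out slightly lower.
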